1.3 Clinical Summary

Four pilot clinical studies designed to evaluate the safety and efficacy of different combinations of topical pilocarpine and oxymetazoline ophthalmic solutions for the treatment of presbyopia and hyperopia were conducted between 2011 and 2013 by AltaVista Instituto del Investigación Medica at the clinic of [name] [name] ([name], 2013). The concentration of pilocarpine tested in all 4 studies was 1.0%, while the concentrations of oxymetazoline tested ranged from 0.0125% to 0.125%. Dosing frequency ranged from a single drop to 1 drop 3 times daily for 6 months. In the clinical data reported by AltaVista, topical ocular dosing of a fixed combination of pilocarpine and oxymetazoline solutions in patients resulted in no serious adverse events. In a study of 65 patients who used a fixed

combination of pilocarpine 1.0% and oxymetazoline 0.0125% up to 3 times daily for 6 months, 3 patients (4.6%) discontinued use of the drops due to brow ache or ocular pain ([name], 2013). This incidence is much lower than the reported 20% to 25% discontinuation rate with pilocarpine monotherapy for glaucoma and suggests that the administration of oxymetazoline with pilocarpine may improve the tolerability profile relative to pilocarpine monotherapy (NDA 200-890; Tsai and Forbes, 2009). Minor, infrequent adverse events were also reported, including a sense of decreased illumination and ocular floaters. AltaVista also reported that oxymetazoline prolonged the duration of the pilocarpine-induced improvement in uncorrected near visual acuity (UNVA) from approximately 4 to 6 hours, with the greatest difference (approximately 1 line) between the combination and pilocarpine monotherapy observed at 6 hours after dosing.

Allergan Study 199201-007 evaluated the safety and efficacy of oxymetazoline (0.125%) and pilocarpine (1.0%) in a multicenter, double-masked, randomized, vehicle-controlled study in patients with presbyopia. Oxymetazoline 0.125% and pilocarpine 1.0% ophthalmic solutions were concurrently administered as an “unfixed combination” in which the medications were administered separately. For all treatment groups, study medications were dosed QD for 3 days, and after a 5 ± 2 -day washout period, BID for 3 days. All dosing was performed by trained personnel in the clinic.

A total of 65 patients were randomized, enrolled, and treated in this study. Fifteen patients were randomized to Group 1 (oxymetazoline [0.125%] dosed in the nondominant eye), 17 to Group 2 (pilocarpine [1.0%] dosed in the nondominant eye), 16 to Group 3 (oxymetazoline [0.125%]/pilocarpine [1.0%] dosed in the nondominant eye), and 17 to Group 4 (oxymetazoline [0.125%]/pilocarpine [1.0%] dosed in OU). In each group, patients were evenly distributed among the 4 strata of iris color and age. Sixty-three of the 65 patients (96.9%) completed the study. One patient in Group 2 and 1 patient in Group 4 discontinued from the study, both due to a nonocular adverse event. There were no statistically significant differences among the treatment groups in any of the demographic variables.

Concurrent dosing of pilocarpine and oxymetazoline provided a statistically significant greater response over vehicle in the percentage of patients achieving at least a 2-line improvement in mesopic, high contrast UNVA at a majority of timepoints postdose in the nondominant eye following both QD and BID dosing regimens. Pilocarpine monotherapy provided a statistically significant greater response over vehicle in the percentage of patients achieving at least a 2-line improvement in mesopic, high-contrast UNVA at a majority of timepoints postdose in the nondominant eye following QD dosing and was numerically superior following BID dosing. Across all timepoints and visits, the mean change from

baseline in lines of UNVA numerically favored the combination groups over pilocarpine monotherapy at later timepoints postdose (hour 8 of the QD dosing period and hour 11 of the BID dosing period), replicating the findings reported by AltaVista. Oxymetazoline monotherapy was found to have little effect on UNVA.

The greatest differences in favor of the combination of pilocarpine and oxymetazoline dosed in the nondominant eye (Group 3) relative to pilocarpine monotherapy dosed in the nondominant eye (Group 2) were seen with more stringent response criteria, most notably with the percentage of patients achieving at least a 3-line gain in UNVA from baseline at all timepoints postdose at the end of both the QD (31.3% versus 11.8%) and BID (12.5% versus 0%) dosing regimens, and in younger patients (ie, the 40- to 47-year age cohort per the prespecified cutoff) who robustly responded to combination with 2.8 to 3.8 lines of improvement on average. Younger patients on pilocarpine monotherapy responded with 1.2 to 2.5 lines of improvement on average. In older patients (ie, the 48- to 55-year age cohort per the prespecified cutoff), the difference was less pronounced between combination therapy and pilocarpine monotherapy. Both pilocarpine monotherapy and concurrent dosing of pilocarpine and oxymetazoline significantly reduced pupil diameter, with a maximal effect at approximately 1 hour postdose (range across visits: -2.56 to -2.73 mm) and a reduced effect 6 to 8 hours postdose (range across visits: -1.05 to -1.66 mm). Combined, these results suggest that in younger patients, the combination may be having a direct effect upon accommodation, providing a benefit over pilocarpine monotherapy for the treatment of presbyopia.

Oxymetazoline monotherapy, pilocarpine monotherapy, and concurrent dosing of pilocarpine and oxymetazoline in 1 or OU were found to be safe and well tolerated. No meaningful difference was seen between groups in the discontinuation rate or the incidence or severity of adverse events, with the exception of “eyelid retraction” that occurred most frequently in the oxymetazoline monotherapy group. No meaningful differences were seen between groups in visual analog scale (VAS) scores for temporal or supraorbital headache. It may require a larger sample size to detect ocular adverse events associated with pilocarpine monotherapy and to properly test AltaVista’s finding of improved tolerability with the combination of oxymetazoline and pilocarpine relative to pilocarpine monotherapy.

The overall objective of this clinical development program is to develop a fixed-dose combination of oxymetazoline and pilocarpine for the treatment of presbyopia. To date, preclinical studies in rabbits and nonhuman primates, 4 pilot clinical studies conducted by AltaVista Instituto del Investigation Medica at the clinic of [name], and Study 199201-007

conducted by Allergan support the combination of pilocarpine and oxymetazoline for the treatment for presbyopia.

1.4 Rationale for Study Design

The current phase 2 clinical study is designed to evaluate the safety, efficacy, and tolerability of fixed combinations of AGN-199201 and AGN-190584 over a 42-day observation period when administered QD, bilaterally, for 28 days in patients with presbyopia.

Additionally, this study will evaluate the safety, efficacy, and tolerability of a fixed combination of AGN-199201 [REDACTED] and AGN-190584 [REDACTED] when administered monocularly to the nondominant eye versus bilaterally for 28 days in patients with presbyopia. The most widely used non-spectacle methods of presbyopia correction use is monovision. In this technique, the eyes are dissociated by focusing 1 eye for distance vision and 1 eye for near vision. Unfortunately, a significant proportion of patients cannot tolerate monovision (ie, ~ 40% for contact lenses and ~ 10% for laser treatments). A pharmaceutical treatment for presbyopia that both increases depth of field by inducing miosis and enhances accommodation may allow patients to dose in 1 or OU without the significant optical limitations faced by current non-spectacle methods of presbyopia correction.

There is widespread belief that prolonged use of decongestant sprays like oxymetazoline can result in a condition of decreased effectiveness called tolerance. It is thought that with time they lose their effectiveness and more and more medication is needed to achieve the same level of decongestion. It has also been proposed that once stopped, the patient experiences rebound congestion ([Vaidyanathan et al, 2010](#)). Extending these finding from nasal application to ophthalmic application, the packaging for Visine LR reads, “overuse may cause more eye redness [rebound congestion].” It is unknown if the findings of tolerance and rebound with extended use of oxymetazoline for eye redness or nasal congestion will impact the efficacy of a fixed combination of AGN-199201 (oxymetazoline HCl ophthalmic solution) and AGN-190584 (pilocarpine HCl ophthalmic solution) for the treatment of presbyopia.

Allergan Study 199201-007 supports the unfixed combination of AGN-199201 [REDACTED] and AGN-190584 ([REDACTED]) as a safe and effective short-term treatment for presbyopia. The current study will evaluate fixed combinations of AGN-199201 and AGN-190584 that include the concentration of AGN-199201 and AGN-190584 that were unfixed and used in Allergan Study 199201-007.

Oxymetazoline systemic exposure has been measured after a single administration of Afrin nasal spray (3 sprays [0.1 mL/spray] in each nostril of 0.05% oxymetazoline, equating to 0.3 mg/dose), which resulted in a mean observed plasma maximum concentration (C_{max}) of 0.245 ng/mL and area under the plasma concentration-time curve from time 0 to 12 hours (AUC_{0-12}) of 1.74 ng·hr/mL [REDACTED]. No serious adverse events were reported in this study, and no patients discontinued prematurely due to an adverse event. There were no notable changes from predose to postdose in clinical laboratory tests, vital sign measurements, electrocardiograms (ECGs), or IOP during the study. This study will determine the systemic pharmacokinetics of AGN-199201 [REDACTED] and AGN-190584 [REDACTED] following single and multiple (QD for 28 days) ophthalmic administrations as a fixed combination in 1 or OU, by analysis of plasma drug concentration-time profiles (C_{max} , time to maximum plasma concentration [T_{max}], and AUC).

2. Study Objectives and Clinical Hypotheses

2.1 Study Objectives

The objectives of this study will be:

- To evaluate the safety, efficacy, and tolerability of fixed combinations of AGN-199201 and AGN-190584 over a 42-day observation period when administered bilaterally QD for 28 days in patients with presbyopia
- To compare the safety, efficacy, and tolerability of a fixed combination of AGN-199201 [REDACTED] and AGN-190584 [REDACTED] when administered monocularly to the nondominant eye versus bilaterally over a 42-day observation period with QD dosing for the first 28 days in patients with presbyopia
- To assess the systemic pharmacokinetics of AGN-199201 [REDACTED] and AGN-190584 [REDACTED] following single and multiple (QD for 28 days) ophthalmic administrations as a fixed combination in 1 or OU, by analysis of plasma drug concentration-time profiles (C_{max} , T_{max} , AUC from time 0 to the last timepoint [AUC_{0-last}], and AUC from time 0 to infinity [AUC_{0-inf}]).
- To evaluate the psychometric properties of the de novo patient-reported outcome (PRO) instruments developed for this program, including the near vision presbyopia performance tasks and task-based questionnaire under mesopic and photopic conditions, the presbyopia patient satisfaction questionnaire, and the presbyopia impact and coping questionnaire

2.2 Clinical Hypotheses

At least 1 fixed combination of AGN-199201 and AGN-190584 ophthalmic solution dosed bilaterally QD for 28 days:

1. will demonstrate a significant improvement in UNVA over vehicle.
2. will demonstrate acceptable safety and tolerability findings.
3. will demonstrate an acceptable pharmacokinetic profile for AGN-199201 and AGN-190584 after single and repeat administrations.

The fixed combination of AGN-199201 [REDACTED] and AGN-190584 [REDACTED] can be administered either in the nondominant eye only or bilaterally for 28 days in patients with presbyopia without any significant difference in the observed safety, efficacy, tolerability or pharmacokinetic profiles.

3. Study Design

This multicenter, double-masked, randomized, parallel-group, vehicle-controlled study will be a controlled comparison of fixed combinations of AGN-199201 and AGN-190584 at different concentrations to vehicle dosed in OU, and the fixed combination of AGN-199201 [REDACTED] and AGN-190584 [REDACTED] dosed in OU or in the nondominant eye only. Study medication will be administered QD in the morning. During office visits 1 through 5, study medication will be administered at hour 0 (8 AM \pm 1 hour). Following the treatment period, all patients will be seen for a 14 \pm 2-day follow-up period as shown in Figure 1. The study duration will be 38 to 65 days per patient.

4. Study Population and Entry Criteria

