- To assess the systemic pharmacokinetics of AGN-199201 [REDACTED] and AGN-190584 [REDACTED] following single and multiple (QD for 28 days) ophthalmic administrations as a fixed combination in 1 or both eyes (OU), by analysis of plasma drug concentration-time profiles (maximum observed plasma concentration-time [C_{max}], time to maximum observed plasma concentration-time [T_{max}], area under the plasma concentration curve from time 0 to the last timepoint [AUC_{0-last}], and area under the plasma concentration-time curve from time 0 to infinity [AUC_{0-inf}])
- To evaluate the psychometric properties of the de novo patient-reported outcome (PRO) instruments developed for this program, including the near vision presbyopia performance tasks and task-based questionnaire under mesopic and photopic conditions, the presbyopia patient satisfaction questionnaire, and the presbyopia impact and coping questionnaire

Clinical Hypotheses:

At least 1 fixed combination of AGN-199201 and AGN-190584 ophthalmic solution dosed bilaterally, QD for 28 days:

1. will demonstrate a significant improvement in uncorrected near visual acuity (UNVA) over vehicle.
2. will demonstrate acceptable safety and tolerability findings.
3. will demonstrate an acceptable pharmacokinetic profile for AGN-199201 and AGN-190584 after single and repeat administrations.

The fixed combination of AGN-199201 [REDACTED] and AGN-190584 [REDACTED] can be administered either in the nondominant eye only or bilaterally for 28 days in patients with presbyopia without any significant difference in the observed safety, efficacy, tolerability, or pharmacokinetic profiles.

Study Design:

Structure: Multicenter, double-masked, randomized, parallel-group, vehicle-controlled

Duration: 38 to 65 days per patient

Study Treatment Groups: See Table 1.

- Group 1: Vehicle Control, OU
 Group 2: Fixed combination AGN-199201 [REDACTED] and AGN-190584 [REDACTED] OU
 Group 3: Fixed combination AGN-199201 [REDACTED] and AGN-190584 [REDACTED], OU
 Group 4: Fixed combination AGN-199201 [REDACTED] and AGN-190584 [REDACTED] OU
 Group 5: Fixed combination AGN-199201 [REDACTED] and AGN-190584 [REDACTED], nondominant eye and vehicle to the dominant eye

Table 1 Study Treatment Groups

Group	AGN-199201 (%)	AGN-190584 (%)	Dosing
1	Vehicle control	Vehicle control	OU
2	[REDACTED]	[REDACTED]	OU
3	[REDACTED]	[REDACTED]	OU
4	[REDACTED]	[REDACTED]	OU
5 ^a	[REDACTED]	[REDACTED]	Nondominant eye

OU = both eyes

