5.4 Treatment Allocation Ratio and Stratification

Patients will be randomized in a 1:1:1:1:1 ratio into 1 of 5 treatment groups:

- Group 1: Vehicle control, OU
- Group 2: Fixed combination AGN 199201 (██████████) and AGN 190584 (██████████), OU
- Group 3: Fixed combination AGN 199201 (██████████) and AGN 190584 (██████████), OU
- Group 4: Fixed combination AGN 199201 (██████████) and AGN 190584 (██████████), OU
- Group 5: Fixed combination AGN 199201 (██████████) and AGN 190584 (██████████),
monocular dosing to the nondominant eye and vehicle to the dominant eye

Randomization will be stratified by age (2 groups: ≤ 50 and > 50) and iris color (2 groups: brown and not brown) at the baseline visit. There will be a total of 4 strata; brown eyes and age ≤ 50 years, brown eyes and age > 50 years, not brown eyes and age ≤ 50 years, and not brown eyes and age > 50 years. For the determination of stratification group assignment for each patient, sites will be required to enter iris color (ie, brown, blue, green, gray, or hazel) and age into the Interactive Response System (IxRS), and the IxRS will assign the stratum.

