7.2 Collection and Derivation of Primary and Other Efficacy Assessments

7.2.1 Primary Efficacy Variable

The primary efficacy variable will be the weighted average change from baseline in mesopic, high contrast UNVA lines at day 28 in the nondominant eye. Baseline will be the hour 0 measure at day 1.

[REDACTED]

[REDACTED]

[REDACTED]

[REDACTED]

[REDACTED]

[REDACTED]

[REDACTED]

[REDACTED]

[REDACTED]

[REDACTED]

[REDACTED]

[REDACTED]

[REDACTED]

[REDACTED]

[REDACTED]

[REDACTED]

[REDACTED]

[REDACTED]

[REDACTED]

[REDACTED]

[REDACTED]

[REDACTED]

Approval Date: 18-Aug-2016

- [REDACTED]
- [REDACTED]
- [REDACTED]
- [REDACTED]
- [REDACTED]
- [REDACTED]
- [REDACTED]

- [REDACTED]
 - [REDACTED]
 - [REDACTED]
 - [REDACTED]
 - [REDACTED]
 - [REDACTED]
 - [REDACTED]
 - [REDACTED]
 - [REDACTED]
 - [REDACTED]

- [REDACTED]
 - [REDACTED]
 - [REDACTED]
 - [REDACTED]
 - [REDACTED]
 - [REDACTED]
 - [REDACTED]
 - [REDACTED]
 - [REDACTED]

Approval Date: 18-Aug-2016

- █ [REDACTED]
- █ [REDACTED]
- █ [REDACTED]
- █ [REDACTED]
 - █ [REDACTED]
 - █ [REDACTED]
 - █ [REDACTED]
 - █ [REDACTED]
 - █ [REDACTED]

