7.3.1 Primary Efficacy Analyses

For the primary efficacy analysis, the weighted average change from baseline will be analyzed by ANCOVA with treatment group, age group, and iris color as fixed effects. A detailed algorithm for the derivation of the primary efficacy variables will be documented in the AP.

█ [REDACTED]

█ [REDACTED]

█ [REDACTED]

█ [REDACTED]

Approval Date: 18-Aug-2016

[Redacted text block]

[Redacted text block]

[Redacted text block]

[Redacted text block]

[Redacted text block]

[Redacted text block]

[Redacted text block]

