7.5 Sample Size Calculation

A sample size of approximately 150 patients will be randomized in a 1:1:1:1:1 ratio into 1 of the 5 study groups. Approximately two-thirds of the enrolled patients will be younger patients (≤ 50 years old), and approximately one-third of the enrolled patients will be older patients (> 50 years old).

Approval Date: 18-Aug-2016

From the Study 199201-007 results, the treatment effect for the younger patients was on average 1.98 lines of change in mesopic, high contrast UNVA, with standard deviations for active and vehicle of 1.12 and 1.01, respectively. For older patients, the treatment effect was on average 0.72 lines of change in mesopic, high contrast UNVA, with standard deviations for active and vehicle of 1.87 and 1.15, respectively. The treatment effect for the younger patients was on average 1.02 lines of change in photopic, high contrast UNVA, with standard deviations for active and vehicle of 1.42 and 0.67, respectively. For older patients, the treatment effect was on average 0.27 lines of change in photopic, high contrast UNVA, with standard deviations for active and vehicle of 1.10 and 0.93, respectively.

Accounting for a 12.5% dropout rate, 26 patients per treatment group will provide 99% power to observe a difference between an active group and the vehicle group for ≥ 1 line of change from baseline in mesopic, high contrast UNVA and 68% power for ≥ 1 line of change from baseline in photopic, high contrast UNVA, with a type 1 error of 0.05.

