4.2 Study Objectives

[figure not shown]
Each study primary objective (PO), and secondary objective (SO) are presented below:

Table 4-2 Study Objectives

[figure not shown]
| Objectives |
|--|
| PO To evaluate the safety, efficacy, and tolerability of fixed combinations of AGN-199201 and AGN-190584 over a 42-day observation period when administered bilaterally, once daily (QD) for 28 days in patients with presbyopia |
| SO1 To compare the safety, efficacy, and tolerability of a fixed combination of AGN-199201 ██████████ and AGN-190584 ██████████ when administered monocularly to the nondominant eye versus bilaterally over a 42-day observation period with QD dosing for the first 28 days in patients with presbyopia |
| SO2 To assess the systemic pharmacokinetics of AGN-199201 ██████████ and AGN-190584 ██████████ following single and multiple (QD for 28 days) ophthalmic administrations as a fixed combination in 1 or both eyes (OU) |
| SO3 To evaluate the psychometric properties of the de novo patient-reported outcome (PRO) instruments developed for this program, including the near vision presbyopia performance tasks and task-based questionnaire under mesopic and photopic conditions, the presbyopia patient satisfaction questionnaire, and the presbyopia impact and coping questionnaire |

[figure not shown]
PO = primary objective, SO1 = first secondary objective, SO2 = second secondary objective, SO3 = third secondary objective

[figure not shown]

[figure not shown]

[figure not shown]

[figure not shown]

5. Statistical Methodology and Study Endpoints

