5.1.1.1.3 Statistical Methodology

The methodologies defined below apply as specified to individual endpoints defined in this SAP. When indicated, 95% two-sided confidence intervals and two-sided p-values will be presented. Individual endpoint analyses may specify exceptions (additions or deletions) to these general definitions.

Table 5-2 Statistical Methodology

| Methodology | Description |
|-----------------------------|---|
| M1 Categorical counts | 
 Number of patients in individual categories 
 Patients with ≥ 1 qualifying event counted once per individual category |
| M2 Categorical descriptives | 
 Number and percentage of patients in individual categories 
 Patients with ≥ 1 qualifying event counted once per individual category (Optional) N included if percentage denominator \neq number of patients in the population (standard percentage denominator). |
| M3 PCS descriptives | 
 Number and percentage of patients meeting potentially clinically significant (PCS) criteria 
 Patients with ≥ 1 qualifying event counted once per PCS category Percentage denominator = number of patients with non-missing baseline and ≥ 1 non-missing postbaseline assessment Unevaluable assessments considered missing |
| M4 Continuous descriptives | 
 N included, mean, standard deviation (SD), median, minimum, maximum N included = patients with non-missing value |
| M5 CFB descriptives | 
 Continuous descriptives for baseline, postbaseline, and change from baseline (CFB) values N included = patients with non-missing values at both baseline and the specified postbaseline analysis visit |
| M6 CFB ANCOVA | 
 Continuous descriptives and standard error (SE) for baseline, postbaseline, and CFB values Estimates derived from mixed model for CFB value controlling for treatment group and covariates (baseline UNVA severity, iris color and age group) 
 Least squares (LS) means and standard errors P-values and confidence intervals from contrast t-test comparing active AGN-199201 treatment groups vs AGN-199201 vehicle N included = patients with non-missing values at both baseline and the postbaseline analysis visit |

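### Protocol 2.2 and the Protocol Summary frame monocular versus bilateral dosing as an absence of significant difference, which does not show similarity at any sample size; no margin or power for the comparison is legible

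*Protocol*

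**What the plan says.** Protocol 2.2 (Clinical Hypotheses) states that the fixed combination used in Group 5 can be given monocularly or bilaterally for 28 days "without any significant difference in the observed safety, efficacy, tolerability or pharmacokinetic profiles". The Protocol Summary repeats the sentence with one added comma: "without any significant difference in the observed safety, efficacy, tolerability, or pharmacokinetic profiles".

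The comparison is also an objective. Protocol 2.1 and the first secondary objective in SAP 4.2 set out to compare safety, efficacy and tolerability "when administered monocularly to the nondominant eye versus bilaterally over a 42-day observation period".

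The regimens differ in one eye. Group 5 receives "monocular dosing to the nondominant eye and vehicle to the dominant eye" (Protocol 5.4), while the bilateral groups receive active drug in both eyes. The primary variable is the change in "mesopic, high contrast UNVA lines at day 28 in the nondominant eye" (Protocol 7.2.1; SAP Table 5-14 names the same eye).

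The power statement concerns vehicle only: "26 patients per treatment group will provide 99% power to observe a difference between an active group and the vehicle group" (Protocol 7.5; SAP 5.1.2 is similar). The legible contrasts in SAP Table 5-2, for the change-from-baseline model (M6) and the responder method (M8), are also active against vehicle. SAP 5.1.1.1.3 lets individual endpoints add to these methods, and Protocol 7.3 allows two-sample between-group tests. Parts of Protocol 7.2 and 7.3 and of the SAP efficacy tables are redacted.

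**The concern.** A hypothesis of no significant difference reverses the usual burden of proof. A noisier or smaller trial is more likely to satisfy it, because a wide confidence interval makes non-significance easy to reach. No other criterion for similarity is legible.

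The choice of eye matters as well. The nondominant eye receives active drug under both regimens, so the primary variable says little about the dominant eye, where dosing differs. Section 2.2 speaks of efficacy without limiting it to an eye.

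At stake is what is concluded about one-eye or two-eye use. An inconclusive comparison could be read as meeting the stated hypothesis although the data leave a clinically relevant difference open.

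**Working it through.** **Inputs** (Protocol 7.5 unless noted)
- Mesopic effect, active minus vehicle: 1.98 lines (younger), 0.72 (older).
- Mesopic SDs, active / vehicle: 1.12 / 1.01 (younger), 1.87 / 1.15 (older).
- Age mix 2/3 younger, 1/3 older. 26 per group. Type 1 error 0.05, two-sided (SAP 5.1.1.1.3).

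**Step 1. Reproduce the plan's own power (active against vehicle).**
- Effect = (2/3)(1.98) + (1/3)(0.72) = 1.56 lines.
- Active variance within age groups = (2/3)(1.12²) + (1/3)(1.87²) = 2.002. Vehicle = (2/3)(1.01²) + (1/3)(1.15²) = 1.121.
- Spread of the effect between age groups, active arm = (2/9)(1.98 − 0.72)² = 0.353.
- SD = √[(2.002 + 0.353 + 1.121)/2] = 1.318.
- Two-sample t-test, 26 per arm: power 98.7%, against the stated 99%.
- The same steps for photopic UNVA (effect 0.77, SD 1.109) give 69.0%, against the stated 68%.

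The inputs are therefore read correctly. These powers apply to effects of 1.56 and 0.77 lines against vehicle and do not carry over to a comparison of two active arms.

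**Step 2. Precision of monocular against bilateral.** Assume that both arms have the age-weighted active SD, √2.002 = 1.415.
- Standard error = 1.415 × √(2/26) = 0.392.
- 95% half-width = t(0.975, 50 df) × SE = 2.009 × 0.392 = 0.79 line.

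**Step 3. Chance of a non-significant result** (noncentral t, 50 df).

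| SD assumed | 95% half-width | True 0.5 line | True 0.75 line | True 1 line |
|---|---|---|---|---|
| 1.12 (younger) | 0.62 | 65% | 34% | 12% |
| 1.415 (age-weighted) | 0.79 | 76% | 53% | 30% |
| 1.87 (older) | 1.04 | 84% | 71% | 53% |

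**Step 4. What a non-significant result leaves open** (SD 1.415).
- Observed difference of zero: the interval reaches 0.79 line, and 0.79/1.56 = 51% of the planning effect.
- Result just short of significance: the far limit is about 2 × 0.79 = 1.58 lines, and 1.58/1.56 = 101%.

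**Step 5. Does the choice of model change this?** The protocol's primary variable "will be analyzed by ANCOVA with treatment group, age group, and iris color as fixed effects". A five-arm model with an age-group term has residual SD √[(4 × 1.415² + 1.059²)/5] = 1.351, where 1.059 is the vehicle SD (√1.121). With 122 df the half-width is 0.74. A two-arm t-test with no age adjustment has SD √(2.002 + 0.353) = 1.535 and half-width 0.86. Across these models a true 0.5-line difference is non-significant in 74 to 79% of trials and a 1-line difference in 25 to 37%. The choice of model matters less than the SD range in Step 3.

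**The case against.** **Status of the sentence.** It stands under clinical hypotheses in a phase 2 study, speaks of observed profiles, and the SAP objective only says to compare. No legible analysis tests for similarity or ties a decision to it. This limits the severity. It does not cure the wording: the same section uses *significant* for improvement over vehicle, so a reader will take it statistically.

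**Redaction.** A margin, a contrast or a named eye may lie in redacted text. That stands, and the absence is claimed only for legible text. A reader might infer that no monocular-bilateral contrast is planned; the documents do not support this, because Protocol 7.3 and SAP 5.1.1.1.3 leave room for one. A contrast alone would still not make a p-value above 0.05 evidence of similarity.

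**Sample size.** A reader might infer that 26 per arm is too few for any similarity claim. That goes too far. The flaw lies in the criterion, at any sample size. With a margin, the answer depends on margin and SD. As an illustration, non-inferiority at one-sided 0.025 with a true difference of zero has power 72% for a 1-line margin at SD 1.415 (90% at SD 1.12), but 25% for a 0.5-line margin at SD 1.415.

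**The eye.** A reader might also infer that the plan names no eye. It does: 2.2 names the dosed eye, and Protocol 7.2.1 and SAP Table 5-14 name the measured eye for the primary variable. What is missing from legible text is the eye measured for this comparison.

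**The SDs.** Study 199201-007 gave the two drugs separately over 3-day dosing periods, with a prespecified age split at 47/48, not 50/51. Protocol 7.5 does not say which split its SDs use, or whether they describe an average over timepoints. M6 also adjusts for baseline severity ("controlling for treatment group and covariates (baseline UNVA severity, iris color and age group"), which is not modelled here and could narrow the interval. Dropout is expected to be below 12.5%, so slightly more than 26 may be evaluable. These points justify the wide SD range.

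**Conclusion.** Wrong as written; minor to moderate. Non-significance cannot support the monocular-bilateral hypothesis at any sample size, and the legible text supplies no margin, no power and no measured eye for it.

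The size rests on three assumptions: Study 199201-007 active SDs in both arms, 26 evaluable patients per arm, and nondominant-eye mesopic UNVA as the measure. On these, a real difference of half a line would usually be missed, and one of a full line missed in roughly three trials in ten. It would be tempting to say that any non-significant result limits the difference to about half of the planning effect. That holds only for an observed difference of zero; a just non-significant result leaves about the whole of it open.

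No figure here covers safety or tolerability, or pharmacokinetics, which the SAP Introduction assigns to a separate plan. The primary comparison with vehicle is unaffected.

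**What to change.** Replace the sentence in Protocol 2.2 and in the Protocol Summary with estimation. Suggested text: *The difference between Group 5 and the bilateral group given the same concentrations will be estimated with a 95% confidence interval for UNVA in the nondominant eye and, where collected, separately for the dominant eye or binocularly. Safety and tolerability will be described by regimen. No similarity conclusion will be drawn from a non-significant p-value; any similarity claim requires a prespecified, justified margin.*

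Then check the unredacted SAP for this contrast, and add it to M6 and M8 only if it is absent.

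The cost is one sentence in two places and one check, with no new patients, data or change to randomization. The downside for the sponsor is that an inconclusive comparison can no longer be reported as similarity.
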